13.2 Variables for Analysis

Key demographic, baseline and peri-operative characteristics will be summarized for the *Allofit* IT Acetabular Shell with a *Longevity* Liner, both overall, and for each investigative site. Demographic, baseline, and peri-operative data will include:

- Demographics
- Age
- Gender
- Body Mass Index
- Alcohol use
- Tobacco use
- Baseline Characteristics
- Preoperative Harris Hip Pain Score
- Preoperative Harris Hip Functional Score
- Preoperative Activity Level
- Concomitant Medication
- Preoperative Radiographic assessment
- Diagnosis
- Oxford Patient Satisfaction
- Peri-Operative
- Surgery time
- Blood loss
- Hospital stay - defined as the date of discharge minus the date of surgery

Summaries will be done and compared preoperatively and at 6-12 weeks, 12 months, and 24 months initially. Long-term follow-up will be further compared at 3, 5, 7, and 10 years postoperatively.

For dichotomous variables and for variables with more than two responses, the number and percentage of patients in each category will be presented for the treatment. For continuous variables, descriptive statistics including counts, means, medians, standard deviations, minima, and maxima will be presented for the treatment group.

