APPENDIX D	INVESTIGATOR'S CONSENT TO THE CLINICAL INVESTIGATION PLAN..	63

1 Contact Information/ List of Investigators

Sponsor:	Zimmer GmbH
Clinical Investigators:	See Appendix A

Clinical Study Manager:	[name], CRA
On-site Monitoring:	[name], CRA
Data-Management:	Zimmer Warsaw
Statistical Analysis:	Zimmer Warsaw and Winterthur
Quality Assurance:	[name], Director Intl Clinical Affairs

[figure not shown]
2 Study Synopsis

Title:	
Allofit® IT with HXPE in Total Hip Arthroplasty
 
A multi-center, prospective, non-controlled post market surveillance study

Sponsor:	Zimmer GmbH
Objectives/ Endpoints:	
The objectives of this study are to obtain survival and outcome data on the Allofit IT Shell in combination with the Longevity® Liner when used in primary total hip arthroplasty. This will be done by analysis of standard scoring systems, radiographs and adverse event records. Data will be used to monitor pain, mobility and survivorship, and to confirm the safety and performance of the Allofit IT HXPE Bearing System.
 
Safety will be evaluated by monitoring the frequency and incidence of adverse events.
 
Performance will be determined by comparing the overall pain and functional performances, survivorship, subject quality-of-life and radiographic parameters of study subjects who received the Allofit IT HXPE Bearing System.
 
Pain and functional performance will be measured using the Harris Hip Score, survivorship will be based on removal or intended removal of the device, subject quality-of-life will be determined by evaluation of the Oxford Hip Score, and radiographic parameters by analysis of x-rays.

Indication/ Target Popula- tion:	Patients, suffering from severe hip pain and disability requiring total hip arthroplasty, who meet the inclusion/ exclusion criteria (see Section 8).
Study Design:	Multi-center, prospective, non-controlled
Clinical Phase:	Post-market
Number of Sub- jects:	A total of 200 patients will be enrolled in this study
Length of Study:	12 years (2 year enrollment plus 10 years follow-up): follow-up visits at 6 months, 1, 2, 3, 5, 7, and 10 years post-operatively.
Study Device:	Allofit IT Shell in combination with:

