	
HXPE Articulation: Longevity Liner with either Metal or Ceramic compatible Femoral Heads
 
Femoral Component: Alloclassic® Zweymüller Hip Stem or CLS® Spotorno®, Avenir® [name] Stem, or Fitmore® Stem
 
Scores: Harris Hip Score (HHS); Oxford Hip Score; EuroQol (EQ-5D)
 
Safety Assessments: Safety will be assessed by appropriate recording and reporting of adverse events throughout the study. All system components are CE marked and commercially available.
 
Statistical Analysis: Data collected will be summarized and reported to each participating Investigator. Statistical analysis is conducted by Zimmer or its designee.
 
Documentation: Paper / electronic

--	---

This Clinical Investigation Plan is written in accordance with the ISO 14155 Standard for the Clinical Investigation of Medical Devices (part 1 and 2) [1;2].

3 Study Procedure Flowchart

4 Data Collection Overview

The following table indicates the forms to be completed at a certain time point:

Form Name	Pre-op	Surgery	Immediate Post-op	6 month (\pm 1 month)	1, 2, 3, 5, 7, 10 years post-op (\pm 2 months)
Informed Consent	X				
Inclusion/Exclusion Criteria (pages 1 & 2)	X				
Demographic Evaluation	X				
Operative Information (pages 1 & 2)		X			
Immediate Post-op Evaluation			X		
Physical Exam	X			X	X
Oxford Hip Score	•			•	•
Patient Activity Questionnaire	•			•	•
EQ-5D	•			•	•
Harris Hip Form	X			X	X
Concomitant Medication Record	X			X	X
Radiographic Evaluation (pages 1 & 2)	X	X		X	X
Adverse Event	^	^	^	^	^
Protocol Deviation	^	^	^	^	^
Study Completion	^	^	^	^	^
Explanted Device		^	^	^	^

- X Form completed by Investigator or designee
- Form is completed by patient
- ^ Form is completed when indicated

5 Introduction

Total hip arthroplasty (THA) is a medical procedure where an arthritic, degenerative or fractured total hip joint is replaced with a prosthetic device. Since the inception of modern THA in 1961 [3], THA has become a widely accepted orthopedic procedure. In 2006, 533,000 total hip replacements were performed in Germany, France, Great Britain, and Italy [4] alone after non-operative treatment of a dysfunctional hip had failed to provide relief from painful and debilitating symptoms. Traditionally, THA was performed on patients between 60 and 75 years old [5]. Due greatly to continuous improvement in implant design, the range of THA patients has broadened to include both young and very old patients [5;6].

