7.1 General

The study design is a multi-center, prospective, non-controlled, consecutive cohort post-market clinical follow-up study involving orthopedic surgeons skilled in total hip arthroplasty and experienced with the implants subject of this study. In total, 5 centers will be involved. This number of clinical sites will permit assessment of the consistency among a multitude of Investigators. A total number of 200 subjects will be included in the study. It is anticipated that each clinical site will enroll 40-60 eligible study subjects, who have provided written informed consent.

Ethics Committee (EC) approval for each site has to be obtained prior to conducting this research. Sequentially, all eligible patients will be offered study enrollment at each center to avoid potential selection bias. All potential subjects will be required to participate in an informed consent process and sign an EC approved written informed consent prior to study enrollment. It is anticipated the enrollment period may be 12 months or longer to assure an adequate number of cases at each site.

Each case enrolled will receive an *Allofit* IT HXPE Bearing System. The study is designed to be prospective to ensure that the study population is representative of the type of population that the device is intended to treat. The subjects included will be candidates for an *Allofit* IT HXPE Bearing System. All system components are CE-marked and commercially available. Patients will be selected according to the subject selection criteria described in section 8.

All subjects will undergo preoperative clinical, functional and radiographic evaluations, total hip arthroplasty, immediate post-operative evaluations and post-operative clinical, functional and radiographic evaluations at 6 months (\pm 1 month), 1 year (\pm 2 months), 2 year (\pm 2 months), 3 year (\pm 2 months), 5 year (\pm 2 months), 7 year (\pm 2 months), and 10 year (\pm 2 months).

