10.1 Case Report Forms

The data will be collected on study specific Case Report Forms (CRF) provided by the Sponsor (see Appendix B).

It is a requirement that two sets of CRFs are completed for patients having bilateral hip replacement.

The following information and data will be collected on all hips entered into the study:

The **Inclusion/Exclusion Criteria** Form (form 1) determines if the patient meets all inclusion criteria and none of the exclusion criteria.

The **Demographic Evaluation** Form (form 2) collects demographic data, diagnosis, and relevant medical and surgical history.

The **Operative Information** (form 3A and B) collects details on the surgical approach, anesthesia, OR time, blood loss and the implant components.

The **Immediate Postoperative Evaluation** Form (form 4) is completed at the first post-operative appointment. This form gathers data on length of hospital stay, discharge disposition, and deep vein thrombosis (DVT) prophylaxis.

The **Physical Exam** Forms (form 5) collects the patient weight, leg length discrepancy, Trendelenburg and Charnley Classification.

The **Oxford Hip Score** (form 17) consists of 12 questions specific to the hip and is a patient completed form [42].

The **Patient Activity Questionnaire** (form 7) collects data on patient activity level and patient satisfaction of the outcome. This form is completed by the patient.

The **EQ-5D (EuroQol) Questionnaire** (form 8) is completed by the patient and assesses his/her general health status. The EQ-5D is used to derive a quality of life index used for health economics considerations [41].

The **Harris Hip Form** (form 9) ascertains the patient's level of pain, activity level and post surgical satisfaction. This form should be completed by the Investigator [42].

The **Concomitant Medication(s)** Form (form 10) collects details on the medication given to the patient.

The **Radiographic Evaluation 1 and 2** Form (form 11A and B) is completed by the Investigator or its designee upon review of the protocol required x-rays.

The **Adverse Events Report** (form 12) is completed as needed for each patient complication noted. A separate form is completed for each complication. Multiple complications per visit are to be recorded on one form.

The **Protocol Deviation** Form (form 13) collects information on the reason for the protocol deviation.

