11.7 Surgery until Discharge Assessment

Post-operative management for study subjects will follow the standard-of-care for patients undergoing total hip arthroplasty. Required surgical and discharge data will include, but is not limited to the following:

1. Operative Information Form
2. Immediate Post-op Evaluation Form
3. Radiographs Evaluation Form (supine anteroposterior (AP) view of the operative hip)
4. Adverse Events
5. Protocol Deviations

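### Section 13.2 sets the first post-operative summary at 6-12 weeks, where no score or follow-up x-ray is scheduled, and leaves out the 6-month visit that collects them

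*Combined protocol and SAP*

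**What the plan says.** Section 13.2 (Variables for Analysis) gives the summary time points in two sentences. The first reads "Summaries will be done and compared preoperatively and at 6-12 weeks, 12 months, and 24 months initially". The second reads "Long-term follow-up will be further compared at 3, 5, 7, and 10 years postoperatively". Together they name one pre-operative and seven post-operative points, and 6 months is not among them.

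The visit schedule differs:

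- The synopsis lists "follow-up visits at 6 months, 1, 2, 3, 5, 7, and 10 years post-operatively".
- The Section 4 table, introduced by "The following table indicates the forms to be completed at a certain time point", has a 6-month column (plus or minus 1 month) and no column for 6-12 weeks.
- Section 7.1 plans "immediate post-operative evaluations and post-operative clinical, functional and radiographic evaluations at 6 months", followed by the yearly visits.
- Section 11.8 repeats this schedule for pain, function, quality of life and radiographs. Section 11.10.1 requires standing AP and lateral films at the same visits.

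Before 6 months, the plan provides for the following:

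- Form 4, which according to Section 10.1 "is completed at the first post-operative appointment". Section 10.1 describes its content thus: "This form gathers data on length of hospital stay, discharge disposition, and deep vein thrombosis (DVT) prophylaxis".
- One film, listed in Section 11.7 among the surgery-to-discharge records as "Radiographs Evaluation Form (supine anteroposterior (AP) view of the operative hip".
- Forms completed only when needed: adverse event, protocol deviation, study completion and explanted device.

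**The concern.** An analysis time point should correspond to a visit at which the analysed data are collected. Here the first post-operative time point has no scheduled visit for scores or follow-up films, and the visit that does collect them is not named.

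Three analysts could read 13.2 in three ways. One could show a 6-12 week column with no scores, one could drop 6 months altogether, and one could substitute 6 months without authority from the text.

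There is a possible knock-on effect on Section 13.1, which builds its clinical-success tables on the Harris Hip Score and gives no time points of its own. If the 13.2 list also governs those tables, no hip could be classed a success at the first post-operative point. Only failures by component removal or planned removal could be counted there. The documents do not say whether the 13.2 list governs 13.1, so this consequence is conditional.

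**Working it through.** The plan gives no figure to reproduce on this point. The check sets the analysis time points against the visit windows, the form schedule and the case report forms.

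**1. Does any visit window overlap 6-12 weeks?** The windows come from Sections 4, 7.1 and 11.8. Conversion: 365.25 / 12 / 7 = 4.348 weeks per month.

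| Visit | Window (months) | Window (weeks) | Overlaps 6-12 weeks | Named in 13.2 |
|---|---|---|---|---|
| 6 months | 5-7 | 21.7-30.4 | No | No |
| 1 year | 10-14 | 43.5-60.9 | No | Yes |
| 2 years | 22-26 | 95.7-113.1 | No | Yes |
| 3 years | 34-38 | 147.8-165.2 | No | Yes |
| 5 years | 58-62 | 252.2-269.6 | No | Yes |
| 7 years | 82-86 | 356.6-373.9 | No | Yes |
| 10 years | 118-122 | 513.1-530.5 | No | Yes |

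In months, 6-12 weeks is 6 / 4.348 = 1.4 to 12 / 4.348 = 2.8. The gap to the earliest follow-up window is 21.7 - 12 = 9.7 weeks. Section 13.2 names 6 of the 7 scheduled follow-up visits and adds one point that matches none.

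**2. What is collected, and when?** From the Section 4 table:

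| Column | Scheduled forms | Score forms (Harris Hip, Oxford, EQ-5D, Patient Activity) |
|---|---|---|
| Surgery | Operative Information, Radiographic Evaluation | 0 of 4 |
| Immediate post-op | Immediate Post-op Evaluation (Form 4) | 0 of 4 |
| 6 months | Physical Exam, the four scores, Concomitant Medication, Radiographic Evaluation (7 forms) | 4 of 4 |

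The supine film in Section 11.7 belongs to the surgery-to-discharge period. It is a post-operative baseline film, not a follow-up x-ray.

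Form 4 has no fixed week, so it could be completed at 6-12 weeks. In Appendix B it covers admission and discharge dates, physical therapy, thrombosis and ossification prophylaxis, weight bearing and complications. It carries no score.

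**3. Could a site record a 6-12 week visit?** Eight visible forms in Appendix B have an examination-period field: Forms 5, 7, 8, 9, 10, 11B, 13 and 17. All eight offer 6 Month as the first post-operative choice. None offers 6-12 weeks.

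**4. What would a literal 6-12 week summary contain?** At most it would hold Form 4 items, as-needed form data, and medication dates entered later on Form 10. It would hold no Harris Hip, Oxford, EQ-5D or activity score and no follow-up film.

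**5. After correction.** With 6 months in place of 6-12 weeks, the 13.2 list matches 7 of 7 scheduled follow-up visits.

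**The case against.** The strongest reply is that this is a wording mismatch with little practical risk.

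- **The list is not stated to be exhaustive.** Section 11.8 collects the 6-month data and says in general terms that all subject data enter the analyses of pain, function, survivorship and radiographs; Section 10.6 also promises summary tables. This stands in part: the 6-month data are within the planned analysis. But neither section names 6 months as a summary point, and neither removes the 6-12 week one.
- **The sentence follows a list of demographic, baseline and peri-operative variables, so it may not govern outcomes.** Most of those items are recorded once and cannot be compared at 12 months, 24 months and 3 to 10 years. The sentence makes sense only for repeated measures. It remains true that its reach into the 13.1 success tables is not stated.
- **An analyst would notice.** Probably so, since the forms offer no such visit. That limits the harm but leaves the plan's text wrong.
- **Section 13 never names EQ-5D, so it should not be counted among the missing scores.** On that stricter count the result is 0 of 3 scores before 6 months instead of 0 of 4. The direction is the same.
- **An early visit might appear in the Section 3 flowchart, or in Form 11A, neither of which is visible in the text.** This cannot be strictly excluded. Such a visit would contradict five consistent statements of the schedule and eight forms, and 13.2 would still omit 6 months.

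**Conclusion.** The concern holds, and its severity is minor. Section 13.2 is wrong as written: it names a first post-operative summary point with no scheduled scores or follow-up x-rays, and it omits the one visit of seven that supplies the first of both. The effect is confined to descriptive early-outcome summaries. No bias, precision or error rate changes.

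Confidence is high. The conclusion rests on the visible schedule and forms, and assumes that the flowchart and Form 11A do not add an early scored visit. The effect on the 13.1 success tables follows only if the 13.2 list governs them.

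**What to change.** In Section 13.2, replace 6-12 weeks with 6 months (plus or minus 1 month). The summary points then read pre-operative, 6 months, and 1, 2, 3, 5, 7 and 10 years, in line with Sections 4, 7.1 and 11.8. The documents do not show whether 6-12 weeks was a slip or was meant to describe early records such as Form 4. If an early summary was intended, keep it as an additional point, state which records it uses, and still list 6 months.

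The cost is one phrase in the analysis section, with no new data and no extra visits.

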The subject of this clinical investigation is the *Allofit* IT Shell in combination with the *Longevity* Liners in primary total hip arthroplasty. This system consists of a cementless modular Acetabular Shell, a modular liner, and a modular femoral head. The characteristics of this THA system may allow for reduction in wear and osteolysis as compared to other approved and marketed THA systems and thus increase the expected implant life.

6 Study Objectives

The objective of this study is to obtain survival and outcome data on the *Allofit* IT Shell in combination with *Longevity* Liners in primary total hip arthroplasty. This will be done by analysis of standard scoring systems, radiographs and adverse event records. Data will be used to monitor pain, mobility and survivorship, and to confirm the safety and efficacy of the *Allofit* IT with HXPE in primary total hip arthroplasty.

a) Safety:

Will be evaluated by monitoring the frequency and incidence of adverse events (AE), serious adverse events (SAE), adverse device effects (ADE) and serious adverse device effects (SADE)

b) Efficacy:

Will be determined by comparing the overall pain and functional performances (based on the Harris Hip Scoring system), survivorship, subject quality-of-life and radiographic parameters (radiolucencies, osteolysis, subsidence, cup migration, change in cup angle and change in femoral shaft angle) of study subjects who received the *Allofit* IT Acetabular System

a. Pain and Functional Performance:

Measurements will be based on the Harris Hip Scoring (HHS) System [39]

b. Subject Quality-of-Life:

Will be determined by the Oxford Hip Score [42] and the EQ-5D [41]

c. Radiographic parameters:

X-rays will be evaluated for radiolucencies, cup migration, osteolysis, subsidence, and change in cup angle

d. Survivorship:

Based on removal or intended removal of the device and will be determined using the Kaplan-Meier method

The data will meet Zimmer's obligation to collect device vigilance and post market surveillance information for European regulatory bodies.

7 Study Design

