11.8 Follow-up Procedures (Data Collection)

Data required for completion of the pain, functional and quality-of-life evaluations as well as the radiographic evaluations will be collected postoperatively at 6 months (\pm 1 month), 1 year (\pm 2 months), 2 year (\pm 2 months), 3 year (\pm 2 months), 5 year (\pm 2 months), 7 year (\pm 2 months), and 10 year (\pm 2 months). Post-discharge data collection will include, but is not limited to the following:

1. Physical Exam Form
2. Oxford Hip Score Form
3. Patient Activity Questionnaire Form
4. Harris Hip Form
5. Concomitant Medication Record
6. Radiographs Evaluation Form (standing anteroposterior (AP) and standard lateral views of the operative hip)
7. EQ-5D Form
8. Adverse Event Form (if any)
9. Protocol Deviation Form (if any)
10. Explanted Device Form (if any)
11. Study Completion Form (if the case)

Patient follow-up is expected to continue through 10 years of follow-up for each case although it is expected that a few subjects may succumb to other medical problems or otherwise lost to follow-up prior to completion of the 10 years of follow-up. All subject data will be used in the analysis of overall pain and functional performance, survivorship, and radiographic parameters. Data will continue to be collected until the subject completes the study, is lost to follow-up, one or several devices are removed due to revision, or the study is otherwise closed.

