13.1 Analysis Objectives

The assessment of efficacy for subjects receiving the total hip replacement system will be determined using the overall pain score and functional performance. Clinical success will be defined as a modified Harris Hip score of > 80 that included a rating of 'mild', or 'no pain'; a failure will be defined as a modified Harris Hip score < 80. Any study hip that required a subsequent surgical intervention where a stem head, cup, or liner was removed, or where a removal was planned, was considered a failure regardless of the Harris Hip score. Success rates will be expressed as percentages and primary summary results will be presented in tables which will contain the number and percentage of patients classified as a clinical success for the treatment group.

The assessment of safety will be evaluated by monitoring the frequency and incidence of adverse device effects in investigational subjects. As part of the safety profile, a survival analysis will be done.

The endpoints that contributed to the composite success will be summarized separately, that is, the Harris Hip Scores, both function and pain. Additionally, there are measures of interest which will be used to assess the investigational device such as radiographic success, all components included in the assessment of radiologic success, the Oxford Hip Score patient satisfaction scores, patient activity scores, concomitant medication usage, and incidence of adverse events.

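### Repeated scores are compared only through visit-by-visit summaries, so selective exit can make the 1- to 10-year course look stable or improved

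*Combined protocol and SAP*

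**What the plan says.** Section 13.2 of the combined protocol and SAP sets the time points: "Summaries will be done and compared preoperatively and at 6-12 weeks, 12 months, and 24 months initially". It continues: "Long-term follow-up will be further compared at 3, 5, 7, and 10 years postoperatively". The method for scores is: "For continuous variables, descriptive statistics including counts, means, medians, standard deviations, minima, and maxima will be presented for the treatment group". Section 13.1 adds: "The endpoints that contributed to the composite success will be summarized separately, that is, the Harris Hip Scores, both function and pain". It also brings in the Oxford Hip Score as a further measure of interest.

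Sections 6 and 9.1 list EQ-5D beside the Oxford score as a quality-of-life endpoint, but section 13 does not mention EQ-5D.

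On who contributes data, section 11.8 says: "All subject data will be used in the analysis of overall pain and functional performance, survivorship, and radiographic parameters". It also lists the events that end collection for a case, among them that "one or several devices are removed due to revision, or the study is otherwise closed". Section 13.3 allows for 20% attrition and plans 200 enrolled.

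Sections 6, 9, 11.8 and 13 contain no change score, paired comparison, confidence interval, repeated-measures model or missing-data rule for the scores. Section 10.3 gives each hip its own case ID, and the data collection table in section 4 repeats the Harris, Oxford and EQ-5D forms pre-operatively and at every follow-up visit from 6 months. Change within a hip can therefore be computed from data already planned.

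**The concern.** There is no control group, so the score evidence consists of the course over time. A comparison of visit summaries answers a clear question only if the same hips stand behind each summary. Here the set shrinks, and part of the shrinkage depends on outcome: a hip whose component is removed stops supplying scores. Section 13.3 assumes 90% survival at 10 years, so about 10% × 200 = 20 hips could leave this way. The plan does not say whether they are part of the 20%.

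Section 13.1 counts a revised hip as a failure, but that rule covers only the yes/no clinical success outcome. Nothing says what happens to its Harris, Oxford or EQ-5D values. If the hips that leave were doing worse, a real late decline could be hidden, or a flat course could appear as a small improvement. The counts in the visit table would show n falling, but not what this does to the mean.

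**Working it through.** The plan gives no figure of its own for this comparison. The requirement of 195 in section 13.3 concerns 10-year survival and is not used here.

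**Inputs.** From section 13.3: 200 hips and 20% attrition, so 200 × 0.8 = 160 at year 10 (taking one hip per patient). Assumed, because the documents give none: SD 12 points; correlation r between year 1 and year 10 of 0.3, 0.5 or 0.7; leavers 5 to 10 points below stayers at year 1.

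**Shift in the visit means with no true change.** Let stayers average S at both visits, leavers average S − g at year 1, and a share a leave.
- Year 1 mean: (1 − a)S + a(S − g) = S − a·g.
- Year 10 mean: S.
- Apparent change: +a·g.
- a = 0.20: 0.2 × 5 = 1.0 and 0.2 × 10 = 2.0 points.
- a = 0.10: 0.1 × 5 = 0.5 and 0.1 × 10 = 1.0 point.

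**Precision.** The 160 hips at year 10 are a subset of the 200 at year 1, so the two means are correlated. With dropout at random:
- Difference in visit means: 12·√(1/200 + 1/160 − 2r/200).
- Paired change in the 160 completers: 12·√(2(1 − r)/160).
- Model using all 200 hips: 12·√((1 − r²)/160 + r²/200 + 1/200 − 2r/200).
- Visits treated as independent samples: 12·√(1/200 + 1/160) = 1.27 for any r.

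| r | Visit means | Completers, paired | Model, all hips |
|---|---|---|---|
| 0.3 | 1.09 | 1.12 | 1.08 |
| 0.5 | 0.95 | 0.95 | 0.92 |
| 0.7 | 0.78 | 0.73 | 0.72 |

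The model gains 0.01, 0.03 and 0.06 points of standard error over the visit-mean difference. The possible bias of 1.0 to 2.0 points is one to two standard errors at r = 0.5 (1.0/0.95 and 2.0/0.95), so bias matters more than precision here.

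**Simulation.** 200 hips, about 20% leaving, no true change, results in SD units:
- Leaving depends on the observed year 1 score (r = 0.3, 0.5, 0.7): visit means show a false gain of 0.05, 0.09 and 0.13. Change in completers alone shows a false loss of 0.12, 0.09 and 0.05. A model that uses every hip's year 1 score gives about 0.00.
- Leaving depends on a stable hip level that is not directly observed (r = 0.5, 0.7): visit means show a false gain of 0.11 and 0.15 (0.11 × 12 = 1.3 and 0.15 × 12 = 1.8 points). Completer change gives 0.00. A two-visit model removes roughly a share r of the shift, leaving about 0.11 × 0.5 = 0.06 and 0.15 × 0.3 = 0.05.

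No single method is unbiased under both mechanisms. The all-hips model is exact in the first and leaves a third to a half of the visit-mean shift in the second.

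**The case against.** The strongest reply is that this is a single-arm post-market study. Its main summary is the percentage of clinical successes, its sample size rests on survival, and no hypothesis is stated for mean scores. Revised hips count as failures in the success rate, and survivorship is estimated by Kaplan-Meier, so late device failure appears elsewhere. Section 11.8 expects only a few deaths and losses, and section 11.9 sets out retention steps. The SD, the correlation and the leaver gap are not in the documents, and the sign of the bias depends on leavers being worse. All of this stands. It limits the weight of the point, but none of it corrects the mean scores.

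Three stronger readings are tempting, and the documents do not support them.
- A reader might infer a large loss of precision, 1.27 against 0.95. The figure 1.27 arises only if the two visits are wrongly treated as independent samples, and section 13.2 plans no standard error or test for the scores.
- A reader might infer that the plan rejects within-hip change. It is silent: the meaning of the comparison is not defined, and the list of statistics is not worded as exhaustive.
- A reader might take section 9 as making lasting function the aim of the study. That sentence describes the purpose of the device. Section 6 sets the study's objective as obtaining survival and outcome data.

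It is also fair that a mixed model does not cure exit caused by an unrecorded decline, and that the missing EQ-5D analysis is an omission rather than a faulty comparison.

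**Conclusion.** The point holds as a cheap improvement to supportive outcomes. Followed as written, the plan lets the visit means move with who remains. The shift is +1.0 to +2.0 points at 20% attrition and +0.5 to +1.0 at 10%, if leavers score 5 to 10 points below stayers and nothing truly changes. The exposure is the 1- to 10-year course. The change from pre-op is unlikely to be affected, because entry requires a Harris score below 70 and the gain after surgery should be large against 1 to 2 points. Precision is not a reason for the change: the gain is at most 0.06 points of standard error over the range examined. The size rests on an assumed leaver gap, and the comparison with the standard errors also rests on the assumed SD and correlation. The gap in the text does not depend on these assumptions: no estimate of change and no handling of attrition or revision is stated for the scores, and no analysis at all for EQ-5D.

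**What to change.** Keep the visit-by-visit table. For Harris pain, function and total, the Oxford score and EQ-5D, add the following.
- Estimated change from pre-op and from 1 year, with 95% confidence intervals, from a repeated-measures mixed model on all available visits, with visit as a factor and hip nested in patient. The nesting also covers bilateral patients, who carry two case IDs.
- A statement that the model assumes missingness depends on observed scores.
- A stated treatment, in the score analysis, of hips that exit through revision.
- A table of earlier scores of leavers and stayers side by side, so that the direction and size of any selection can be seen.

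The time points need tidying in the same edit: section 13.2 uses 6-12 weeks, while sections 4, 7.1 and 11.8 place the first scored follow-up at 6 months. These passages must be reconciled.

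The cost is SAP wording and some programming, with no new data. The downside is reliance on a missing-at-random assumption, which the leaver and stayer table helps a reader to judge.
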